## 3.2 Exclusion Criteria

1. Prior invasive malignancy within 2 years except for non-invasive malignancies such as cervical carcinoma in situ, in situ prostate cancer, non-melanomatous carcinoma of the skin, lobular or ductal carcinoma in situ of the breast that has been surgically cured
2. Isolated local recurrence or persistent disease
3. Has disease that is suitable for local therapy administrated with curative intent

4. Severe, active co-morbidity
5. Currently participating in and receiving clinical trial treatment or has participated in a trial of an investigational agent and received study treatment or used an investigational device within 4 weeks of the first dose of treatment
6. Has prior chemotherapy, targeted therapy, or radiation therapy within 2 weeks prior to study Day 1 or who has not recovered ( $\leq$  grade 1 or at baseline) from adverse events due to previous administered agent
7. Untreated active central nervous system (CNS) metastatic disease, lepto-meningeal disease, or cord compression
8. Clinically significant (active) cardiovascular disease: cerebral vascular accident/stroke ( $<6$  months prior to enrollment), myocardial infarction ( $<6$  months prior to enrollment), unstable angina, congestive heart failure ( $\geq$  New York Heart Association Classification Class II), or serious cardiac arrhythmia requiring medication.
9. Prior treatment with any other anti-programmed cell death protein-1 (anti-PD-1), or PD Ligand-1 (PD-L1) or PD Ligand-2 (PD-L2) agent or an antibody targeting other immuno-regulatory receptors or mechanisms
10. Irritable bowel syndrome or other serious gastrointestinal chronic conditions associated with diarrhea within the past 3 years prior to the start of treatment
11. Known history of testing positive for HIV or known acquired immunodeficiency syndrome.
12. On chronic systemic steroid or any other forms of immunosuppressive medication within 14 days prior to the treatment. Except:
  - a. Intra-nasal, inhaled, topical steroids, or local steroid injection (e.g., intraarticular injection);
  - b. Systemic corticosteroids at physiologic doses  $\leq 10$  mg/day of prednisone or equivalent;
  - c. Steroids as premedication for hypersensitivity reactions due to bintrafusp alfa
13. Active or prior documented autoimmune or inflammatory disorders in the past 2 years, except diabetes type I, vitiligo, psoriasis, or hypo- or hyperthyroid diseases not requiring immunosuppressive treatment

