### 5.3 Handling of the Dosage Form

For applications in clinical studies, the freeze-dried drug product must be reconstituted with 4.5 mL of water for injection and further diluted with 0.9% saline solution (sodium chloride injection)

supplied in an infusion bag. The liquid formulation is diluted directly with 0.9% saline solution. The estimated volumes of delivery are anticipated to be either 250 mL or 500 mL, which are clinically acceptable. Detailed information on infusion bags and medical devices to be used for the preparation of the dilutions and subsequent administration, and assigned dose levels and concrete volumes to be replaced to prepare the target doses are described in the Pharmacy Manual.

Bintrafusp alfa 1200mg will be administered intravenously on Day 1 of each 2-week study cycle. Bintrafusp alfa may be administered up to 3 days before or after the scheduled day of administration of each cycle due to administrative reasons.

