### 5.6.7 Management of Treatment-Related Anemia

- Anemia is considered an important identified risk for bintrafusp alfa.
- Hematology assessment must be performed at baseline, prior to each bintrafusp alfa dose, at the end of treatment visit and at 28 ( $\pm 5$  days) days post-treatment safety follow-up.
- Participants must enter the study with Hgb values at least 9g/dl
- All relevant hematological testing for treatment-related anemias should be done prior to a blood transfusion, if clinically feasible

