
In case of rapid decrease of hemoglobin (Hgb), such as a decrease greater than 2.0 g/dL across a 2 weeks period, withhold the subsequent cycles of study intervention until Hgb is stabilized and do a thorough assessment of bleeding (for example, upper and lower GI endoscopy, enhancement CT etc.); if Grade 1 or greater bleeding is observed or suspected, withhold the bintrafusp alfa until the bleeding is resolved/controlled and resume the dose of bintrafusp alfa reduced by 50%. Once Hgb decrease is recovered to <math>\leq</math> Grade 1 or baseline and stably controlled, the Investigator is encouraged to communicate with Medical Monitor to re-escalate the dose. The dose of bintrafusp alfa may be re-escalated to full dose once Hgb is stabilized without further need for blood transfusion in the subsequent cycles. The timing of re escalation may need a case-by-case decision. See Section Table 5 regarding stabilization of anemia.
	
Tumor Bleeding	
Grade $\geq 2$	
 
• Study treatment must be held till the event recovers to Grade <math>\leq 1</math>
 
• Permanently discontinue treatment if the Investigator considers the participant to be at risk for additional severe bleeding.
 

Grade $\geq 3$	
 
• If Grade <math>\geq 3</math> bleeding event had been observed, regardless of causality with the study intervention, upon resumption of the study intervention bintrafusp alfa dose should be reduced by 50%. Once there is stable resolution and no recurrence of bleeding on reduced dose, Investigator is encouraged to communicate with Medical Monitor potential dose re-escalation after careful benefit-risk assessment. Treatment should be permanently discontinued if the Investigator considers the participant to be at risk for additional severe bleeding.
 
• In case of rapid decrease of hemoglobin (Hgb), see Section Mucosal/Non-Tumor bleeding.
 

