## **6 FOLLOW UP AND OUTCOME EVALUATION**

### **6.1 Follow-Up Schedule**

All participants will be followed every 2 weeks during the intervention. At each visit, patient's performance status and toxicity of treatment will be monitored, and blood test will be checked for complete blood count, liver function, and renal function. Thyroid function test and early morning cortisol (9am) will be performed at least every 4 weeks while on bintrafusp alfa therapy. For female patients in reproductive age, urine or serum pregnancy test needs to be performed at least every month while the subject is on bintrafusp alfa therapy. All adverse events and laboratory abnormalities will be graded per the National Cancer Institute Common Terminology Criteria for Adverse Events, version 4.0.

For blood-borne immune markers and exploratory biomarkers, plasma EBV DNA will be determined before treatment and every 2 weeks until disease progression; plasma TGF $\beta$ 1 measurement will be performed every 8 weeks until disease progression; exo-PD-L1 concentration will be measured every 2 weeks until disease progression.

Tumor imaging by CT head, neck, chest, abdomen, and pelvis will be done at baseline, every 8 weeks for the first 12 months, then every 12 weeks thereafter. Response will be assessed per RECIST version 1.1. Treatment decisions will be based on Investigator(s) review.

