## 11 APPENDIX Schedule of Assessments

Procedures	Screening	Treatment Period (bintralusp alfa until PD; unacceptable toxicity; death or withdrawal; maximum of 2 years)										Disease Progression
		Cycle 1 m Cycle = 14 Days ± 7 Days		Cycle 2	Cycle 3	Cycle 4	Cycle 5	Cycle 6	Cycle 7	Cycle 8	Cycle 9 and thereafter	
		Day -28 - 0	Day 1	Day 1	Day 1	Day 1	Day 1	Day 1	Day 1	Day 1	Day 1	
Tests and Observations												
Informed Consent d	x											
Medical History	x											
Physical Examination (including skin examination) e	x	x	x	x	x	x	x	x	x	x	x a	x
Vital Signs	x	x	x	x	x	x	x	x	x	x	x a	x
ECOG Performance Status	x	x	x	x	x	x	x	x	x	x	x a	x
ECG	x	x				x					x b	x
Adverse Event Evaluation	x	x	x	x	x	x	x	x	x	x	x a	x
Concomitant Medication Review	x	x	x	x	x	x	x	x	x	x	x a	x
Laboratory Tests												
CBC f	x	x	x	x	x	x	x	x	x	x	x a	x
Coagulation Test h	x	x	x			x	x	x	x	x	x b	x
Comprehensive Serum Chemistry Panel g	x	x	x	x	x	x	x	x	x	x	x a	x
Exploratory blood-based biomarkers i	x	x i	x	x i	x	x i	x	x i	x i	x	x i	x
Urinalysis	x	x	x	x	x	x	x	x	x	x	x a	x
Pregnancy Test j	x						x				x c	x
Thyroid Function Test		x		x		x		x		x	x c	x
Cortisol 9AM		x		x		x		x		x	x c	x
Disease Assessment												
CT Scan (Head, Neck, Chest, Abdomen, Pelvis) k	x	x				x				x k	x	
MRI Scan (Brain)												
Survival follow-up	x		x				x					x
Quality of life assessment l	x		x				x				x	x

- a. Assessments/procedures are to be performed on Day 1 every cycle and prior to treatment unless otherwise specified.
- b. Assessments and procedures are to be performed on Day 1 every 4 cycles and prior to treatment unless otherwise specified.
- c. Assessments and procedures are to be performed on Day 1 every 2 cycles and prior to treatment unless otherwise specified.
- d. Informed Consent must be obtained  $\leq$  28 days prior to the initiation of trial treatment.
- e. Physical examinations will include measurements of weight and vital signs (resting heart rate, blood pressure, respiratory rate, temperature).

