- f. Hematology parameters include the following laboratory tests: complete blood count with 3-part differential (i.e. total neutrophil count including bands, lymphocytes, and monocytes), hemoglobin, hematocrit and platelets.
- g. Blood chemistry must include glucose, BUN, creatinine (eGFR), sodium, potassium, magnesium, chloride, calcium, CO2, alkaline phosphate, AST (SGOT), total bilirubin, total protein, albumin, phosphorus, uric acid.
- h. Coagulation test include PT, PTT and INR.
- i. Plasma EBV DNA will be determined before treatment and every 2 weeks until disease progression; plasma TGF $\beta$ 1 measurement will be performed every 8 weeks until disease progression; PD-L1 concentration in the exosome will be measured every 2 weeks until disease progression.
- j. Pregnancy test will be performed within 1 week prior to treatment, if a cycle is missed during treatment or pregnancy and at the end of treatment visit only for women of childbearing potential.
- k. Patients will have CT scan at Screening/Baseline ( $\leq$  28 days prior to initiation of trial treatment), every 8 weeks for the first 12 months, and every 12 weeks thereafter. Patients will also have CT scan whenever disease progression is suspected. For patients who discontinue treatment without radiographic progression per RECIST 1.1 (e.g. in patients who discontinue treatment for clinical progression or adverse reactions), disease assessment should continue as stated in schedule until radiographic disease progression or alternate therapy is given.
- l. Quality of life (QoL) will be assessed by patient-reported EORTC QLQ-C30 and H&N-35 questionnaires every 12 weeks in the first year.
- m. If screening assessments were completed within 28 days, they do not need to be repeated on Day 1 of Cycle 1 if patient's condition has not changed.

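### Footnote m lets the first dose be given on blood counts and chemistry up to 28 days old, which conflicts with the per-visit and per-dose testing rules and leaves the haemoglobin-drop rule without a Day 1 starting value

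*Protocol*

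**What the plan says.** In the section 11 grid, CBC and the serum chemistry panel are marked at Screening (Day -28 to 0) and again at Cycle 1 Day 1. Footnote m is attached to the Cycle 1 heading. It provides that screening assessments "completed within 28 days, they do not need to be repeated on Day 1 of Cycle 1 if patient's condition has not changed". It lists no exceptions and does not define the patient's condition.

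Other parts of the protocol address the same tests:

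- Section 6.1, for each visit in a two-weekly schedule during the intervention: "blood test will be checked for complete blood count, liver function, and renal function".
- Section 5.6.7: "Hematology assessment must be performed at baseline, prior to each bintrafusp alfa dose", followed by end-of-treatment and post-treatment time points.
- Section 5.6.5, renal table: serum creatinine is to be monitored ahead of every dose. Hepatitis table: AST, ALT and bilirubin ahead of each infusion.
- Section 5.6.8, on a rapid haemoglobin decrease (repeated in the bleeding table of 5.6.5): "such as a decrease greater than 2.0 g/dL across a 2 weeks period, withhold the subsequent cycles of study intervention until Hgb is stabilized". A bleeding work-up follows, and treatment resumes at half dose if bleeding is observed or suspected.
- Section 3.2, exclusion 6: "Has prior chemotherapy, targeted therapy, or radiation therapy within 2 weeks prior to study Day 1 or who has not recovered", where recovery means to grade 1 or less, or to baseline.

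None of these texts mentions an exception for Cycle 1.

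**The concern.** An unchanged condition is something a clinician can judge at the bedside. A silent fall in haemoglobin or rise in creatinine is not, and the test that would show it is the one being waived. A site that follows footnote m can therefore give dose 1 on values up to four weeks old while departing from 6.1 and from the per-dose lines in 5.6.5.

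The second issue is the starting value for 5.6.8. That rule concerns change over about two weeks and leads to withheld cycles, endoscopy or imaging, and a dose cut. If no count is taken on Day 1, the first on-treatment count has only the screening value to be compared with. Anaemia and bleeding are both adverse events of special interest in section 6.6.3, so this is monitoring that the protocol itself treats as important.

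**Working it through.** No sample size, power or event figure is involved. The check is a comparison of texts plus interval arithmetic.

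**Inputs.** Oldest permitted screening sample: 28 days (footnote m and the screening column). Cycle length: 14 days. Window in the grid: "Cycle = 14 Days ± 7 Days". Window in section 5.3: dosing "may be administered up to 3 days before or after the scheduled day of administration of each cycle". Washout from prior therapy: 2 weeks (exclusion 6).

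**Span of the first haemoglobin comparison.** Span at Cycle 2 Day 1 = age of the last count at dose 1 + days from dose 1 to Cycle 2 Day 1.

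| Last count before dose 1 | Nominal 14-day cycle |
|---|---|
| Day 1 sample | 0 + 14 = 14 days |
| 7 days old | 7 + 14 = 21 days |
| 14 days old | 14 + 14 = 28 days |
| 28 days old | 28 + 14 = 42 days |

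With a Day 1 sample, the visit windows alone give 11 to 17 days (±3) or 7 to 21 days (±7). With the oldest permitted sample, the upper limits are 28 + 17 = 45 days and 28 + 21 = 49 days.

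**What a long span does to the rule.** Write Hs, H1 and H2 for haemoglobin at screening, Day 1 and Cycle 2 Day 1. Without a Day 1 count the site sees only

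Hs − H2 = (Hs − H1) + (H1 − H2).

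The rule is concerned with the last term. If haemoglobin rose before dosing, Hs − H1 is negative, and a post-dose fall above 2.0 g/dL can appear as less than 2.0. If haemoglobin drifted down before dosing, Hs − H1 is positive, and a slow pre-treatment decline can appear as a rapid fall. The two terms cannot be separated from the data collected.

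**Order of screening sample and prior chemotherapy.** Exclusion 6 permits chemotherapy until 14 days before Day 1. A 28-day-old sample can therefore predate it by up to 28 − 14 = about 14 days. Exclusion 6 also requires recovery from the toxicity of that treatment, but a count taken before the treatment cannot show that counts have recovered from it.

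**Text against text.** Section 6.1 attaches CBC, liver and renal tests to each visit, and the grid places Cycle 1 Day 1 within the treatment period with both tests marked. Footnote m removes them. The creatinine and liver lines in 5.6.5 describe monitoring tied to each administration, which a four-week-old value does not provide. Section 5.6.7 names baseline and pre-dose haematology as separate time points, which suggests two samples at the start of treatment but does not say so.

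**The case against.** The strongest reply is that footnote m is a specific, written exception to a general schedule, and that 28 days was chosen deliberately: it is also the limit for consent and CT, while footnote j sets one week where a tighter limit was wanted (the pregnancy test). The waiver is optional, conditional and confined to Cycle 1, and it may have been meant mainly to avoid repeating the CT and ECG. All of that is fair. But the wording is not limited to CT and ECG, and neither 6.1 nor 5.6.5 acknowledges an exception, so a site cannot tell which text governs.

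Three stronger readings are tempting, and the documents do not support them:

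- A reader might infer that footnote m flatly contradicts 5.6.7. It does not: a screening count is, literally, taken before dose 1 and could serve as both baseline and pre-dose value.
- A reader might infer that the 5.6.8 rule fails altogether. It does not: the two-week, 2.0 g/dL fall is given as an example, the grid already allows 7 to 21 days between counts, and a fall measured from screening will often still be seen. Treating such a fall as rapid errs toward holding the drug. What is lost is the timing of the fall and, if haemoglobin rose before dosing, possibly its detection.
- A reader might infer that the protocol permits dosing on pre-chemotherapy counts without safeguard. It does not: exclusion 6 demands recovery, and a careful site would regard new chemotherapy as a changed condition. The footnote simply does not say so.

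**Conclusion.** The point holds as a first-dose safety and consistency defect. As written, footnote m lets CBC and chemistry at dose 1 be up to 28 days old. It stretches the first haemoglobin comparison to as much as 42 days against a nominal 14, and it disagrees with 6.1 and the per-dose lines of 5.6.5. From Cycle 3 onward the comparison returns to the usual interval.

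This rests on two readings. The first is that footnote m means what it says and covers laboratory tests. The second is that the grid as extracted places the marks correctly. The protocol does not say how often the waiver would be used; the only ceiling is the 38 planned patients, which is not an estimate. The objective response rate, its two-stage rule and the sample size are unaffected. It is a cheap improvement that should be made, not a flaw that threatens the trial's conclusions.

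**What to change.** Amend footnote m so that it does not apply to CBC and serum chemistry, and state that both are taken and reviewed before dosing on Cycle 1 Day 1. This brings the footnote into line with 6.1, 5.6.5 and 5.6.7 and gives 5.6.8 a Day 1 starting value (14 days nominal, within the ordinary visit window).

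The cost is at most one routine test per patient at a visit the patient already attends. Thyroid function and morning cortisol are marked at Cycle 1 Day 1 but not at Screening, so footnote m cannot waive them and blood is drawn that day in any case.

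If the investigators want to keep some reuse of screening values, an optional and weaker alternative is to accept them only when taken within 7 days before dose 1 and after the last anticancer treatment. That limits the nominal comparison to 7 + 14 = 21 days. The 7-day figure is a suggestion; the protocol sets no such limit for these tests.
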